**ALLOB-DU1 - Clinical Study Protocol**

ALLOB-DU1\_CSP | V 05 | Author: [name] | February 02, 2017 | Pg. 124/136

documents, memorandum, minutes, reports, correspondence), graphic (including but not limited to drawings, figures, schema or other material) or computer-readable form, will become the property of the Sponsor.

The Investigator, who will have information or data of any kind pertaining to the Study, including but not limited to Study results from individual Study sites, as well as any Sponsor Confidential Information for the purpose of the Study, whether in any and all intangible and/or tangible expressions, in any media, in strict confidence, shall not directly or indirectly publish, communicate, disseminate, display, deliver, distribute, reproduce, disclose, or otherwise make available such information and/or data to any third party prior written approval from the Sponsor.

Publication, communication (including but not limited to abstracts and posters), disclosure, release, or dissemination of any information or data of any kind pertaining to the study, including study results from individual study sites, is however possible in mutual agreement between the Investigator and the Sponsor, provided that:

- Any proposed communication (including, but not limited to abstracts and posters) or publication will be submitted to the Sponsor prior to any submission; and
- Any proposed communication or publication will reflect the collaboration and respective roles of the Investigators, Investigating Sites, and Sponsor's personnel; and
- The Sponsor shall be given thirty (30) days to review communications (abstracts and posters), and sixty (60) days to review publications; and
- In the event that the Sponsor does not object to the proposed communication or publication within thirty (30) days or sixty (60) days of its receipt respectively, as the case may be, it will be deemed to have been approved; and
- In the event that the Sponsor objects to the proposed communication or publication for reasons relating to the patentability of an invention or the protection of any other forms of intellectual property rights that would be disclosed by such proposed communication or publication, then submission of the communication or publication will be delayed for a maximum of six (6) months to enable the Sponsor to protect its rights; and

**ALLOB-DU1 - Clinical Study Protocol**

ALLOB-DU1_CSP	V 05	Author: [name]	February 02, 2017	Pg. 125/136
---------------	------	-------------	-------------------	-------------

- In the event that Bone Therapeutics reasonably objects to the proposed communication or publication as conflicting with or compromising the Sponsor's intellectual property rights or interests, the proposed communication or publication shall be modified in order to fully address the Sponsor's concerns and requests of modifications (including, but not limited to deletion of any Sponsor Confidential Information from the proposed communication or publication), and such modified communication or publication may not be submitted, published, disclosed, or disseminated until the Sponsor has confirmed its agreement in writing; and
- Any objection/requested modification made by the Sponsor concerning a proposed communication or publication shall be implemented.

## ALLOB-DU1 - Clinical Study Protocol

ALLOB-DU1\_CSP

V 05

Author: [name]

February 02, 2017

Pg. 126/136

**ALLOB-DU1 - Clinical Study Protocol**

[figure not shown]
ALLOB-DU1_CSP	V 05	Author: [name]	February 02, 2017	Pg. 132/136
---------------	------	-------------	-------------------	-------------

**15 ANNEXES**

## 15.2 ANNEX 1: VISUAL ANALOGUE SCALE OF GLOBAL DISEASE EVALUATION

In the patient's and Investigator's questionnaires, the Visual Analogue Scale for Global Disease Evaluation is presented as follows:

"Considering (over the last week\*) all the way your disease (i.e., delayed-union fracture) affects you, please indicate by an X on this horizontal line how well you are doing with the worst possible general health (100) and best possible general health (0)."

*\*Or as perceived by the Investigator during the visit*

### 15.3 ANNEX 2: VISUAL ANALOGUE SCALE OF PAIN

In the patient's questionnaires, the Visual Analogue Scale for pain is presented as follows:

"The horizontal line below represents extreme pain (100) and no pain (0). Please indicate on this horizontal line the position reflecting the best your answer to the below question by a X"

[figure not shown]
#### 15.3.1 Pain at rest

On average, how would you qualify your pain at rest over the last week?

[figure not shown]
#### 15.3.2 Pain during activities

On average, how would you qualify your pain during daily life activities over the last week?

#### 15.3.3 Pain at palpation (performed by the Investigator or the nurse)

How would you qualify the pain at palpation?

#### 15.4 ANNEX 3: WEIGHT BEARING SCORE

For a delayed-union fracture of a lower extremity, the patient will be requested to stand or walk.

For a delayed-union fracture of an upper extremity, the patient will be requested, while standing, to push with the injured arm on a table.

The test will be done “as tolerated” by the patient who will complete the questionnaire below according to the fracture site.

Fracture site:

Score	Lower Extremity Long Bones 	Upper Extremity Long bones 
0 	No weight on injured leg is allowed. While the patient stands or walks, he/she must hold leg off the floor.	No weight on injured arm is allowed. While the patient stands, he/she must hold injured arm off the table.
1 	When the patient stands or walks, he/she may only touch the floor for balance. No body weight can be placed on the leg.	When the patient stands, he/she may only touch the table. No body weight can be placed on the arm.
2 	The patient may place some of his/her body weight on the injured leg when he/she stands or walks.	The patient may place some of his/her body weight on the injured arm when he/she stands and leans on the table.
3 	Full weight bearing.	Full weight bearing.

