#### 2.4.2 Clinical Evaluation

In order to avoid bias, clinical evaluation should be the first procedure during a study visit before discussing with the Investigator or the Study Nurse/Coordinator. Indeed, the patient has to complete the questionnaires alone without any outside intervention (Bryant and Fernandes, 2011).

The following clinical assessment will be evaluated:

- Global Disease Evaluation using a Visual Analogue Scale (see details in section 3.2.1 and Annex 1): the Global Disease Evaluation VAS is a 100 mm length horizontal line where 0 means best possible health status (“very well”) and 100 the worst possible health status (“extremely bad”). Patients must mark an “X” on the scale to indicate their general health status over the last week. Principal Investigator (or the study nurse) must mark an “X” on the scale to indicate the general health status of the patient as perceived at the time of the visit.
- Pain using a Visual Analogue Scale (see details in Annex 2): the Pain VAS is a 100 mm length horizontal line with endpoints labelled “no pain” (0) and “extreme pain” (100). Patients must mark an “X” on the scale to indicate their pain over the last week. In this study, pain will be evaluated by the patient at rest, during activity and at palpation (performed by the Investigator or the study nurse).
- Weight-Bearing using a Likert scale (see details in Annex 3): in this study, functionality on the affected limb will be assessed using weight-bearing. In this test, the patient will be asked to place only as much weight as he/she feels comfortable (as tolerated) on the injured limb (based on pain feeling) standing. This specific category allows a differential scoring related to pain feeling.

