## ALLOB-DU1 - Clinical Study Protocol

ALLOB-DU1_CSP	V 05	Author: [name]	February 02, 2017	Pg. 48/136
---------------	------	-------------	-------------------	------------

*Weight-Bearing Score*

The functional evaluation using weight bearing limits or restrictions is based on a semi-quantitative score on the following categories (e.g., University of Pittsburgh, Medical Center info for patients, 2004):

- Non weight bearing (score of 0): no weight on injured arm/ leg is allowed. While the patient stand or walk he/she must hold injured leg/arm off the floor/table.
- Toe-touch or finger-touch weight bearing or touchdown weight bearing (score of 1): when the patient stand or walk, he/she may only touch the floor/table for balance. No body weight can be placed on the leg/arm.
- Partial weight bearing (score of 2): the patient may place some of his/her body weight on the injured leg/arm when he/she stand or walk.
- Full weight bearing (score of 3)

This scoring can be done “unrestricted” or “as tolerated”. In the latter, the patient can place only as much weight as he/she feels comfortable on the injured limb (based on pain feeling). The patient places less weight on the affected limb if he/she feels pain. This specific category allows a differential scoring related to pain feeling (see Annex 3). There is no weight-bearing assessment based on a visual analogue scale.

Unfortunately, weight bearing scoring does not allow the use of validated assessment tools, and the current existing scoring method cannot avoid room for subjective patient and physician interpretation. [REDACTED]

[REDACTED]

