**5.4 Post-operative Management**

Following the implantation procedure and the hospital stay, immobilization and unloading of the treated bone will be requested and all patients will remain non-weight-bearing on the operated limb as long as judged necessary by the Investigator. Progressive mobilization and load bearing will be allowed thereafter.

[REDACTED] (at Visit #3).

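### In Annex 3 a weight-bearing score of 0 can record the post-operative order and not pain-limited function, so scores taken under restriction should be flagged

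*Combined protocol and SAP*

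**What the plan says.** The weight-bearing score is among the clinical efficacy criteria in the protocol synopsis. Section 2.4.2 sets the mode: "the patient will be asked to place only as much weight as he/she feels comfortable (as tolerated) on the injured limb". Section 3.2.1 explains the purpose of that mode: "The patient places less weight on the affected limb if he/she feels pain". Annex 3 repeats that the test is done as tolerated and that the patient fills in the form. Section 2.4.2 adds that "the patient has to complete the questionnaires alone without any outside intervention".

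The printed options come from a different kind of scale. Section 3.2.1 introduces them as "The functional evaluation using weight bearing limits or restrictions" and opens the list with "Non weight bearing (score of 0): no weight on injured arm/ leg is allowed". Annex 3 carries this over for the leg as "No weight on injured leg is allowed. While the patient stands or walks, he/she must hold leg off the floor", with a matching sentence for the arm.

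Section 5.4 states that after implantation and the hospital stay "all patients will remain non-weight-bearing on the operated limb as long as judged necessary by the Investigator", with progressive loading afterwards. The readable text gives no fixed end to that period.

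**The concern.** The stated mode asks what the patient can comfortably bear. Score 0 states what the patient is permitted to do. For a patient still under the Section 5.4 order, that option is literally true whatever the limb would tolerate, and the patient is meant to complete the form without help.

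The study is open and has no control group, so no concurrent arm under the same order shows how much of a change in the score comes from the order. According to the synopsis, baseline clinical assessments belong to Visit #2, when implantation takes place. An early change from baseline could therefore compare a score taken before the post-operative order with one taken under it. What is at stake is how the course of this one criterion across visits can be read.

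**Working it through.** The plan states no figure to reproduce. The check is a comparison of texts, plus a short illustration.

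**1. The option cells (Annex 3: four scores, two limbs, 4 × 2 = 8 cells).**
- Score 0, leg and arm: 2 cells, both worded as a prohibition.
- Scores 1 and 2, leg and arm: 2 × 2 = 4 cells. They use *may* and *can*, which express permission or ability equally well, so they are only ambiguous.
- Score 3, leg and arm: 2 cells, neutral.
- Total 2 + 4 + 2 = 8. Cells that mention pain, comfort or tolerance: 0.

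**2. Two patients, one score.** Patient A is under the order and could place some weight without discomfort. Patient B is under no order and cannot load the limb because it hurts. Option 0 fits both. The score alone cannot tell them apart.

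**3. Change over time (illustration, not data).** Suppose patient A's tolerance stays at level 2 throughout. The score under the order is 0, and after the order is lifted it is 2. The recorded rise is 2 − 0 = 2 points, while tolerance has changed by 2 − 2 = 0. By construction of the scale, the gap between a 0 recorded under the order and the tolerated level lies between 0 and 3 points for one patient.

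**4. Does rewording cure it?** Let option 0 say that the patient holds the limb off the floor or table. Patient A, obeying the order, still does so and still scores 0. The confounding comes from the order. Wording decides only whether the form agrees with its own instruction. Separating A from B requires knowing whether a restriction was in force.

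**5. Is the score taken while the order applies?** The synopsis has efficacy endpoints determined at 2 weeks and at 1, 3 and 6 months. Scoring at the early visits is inferred from that general line, because the visit procedure lists are redacted.

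**6. Where the score is used.** The failure definition (Sections 2.2.2 and 10.5.6.1) uses rescue surgery, the patient's Global Disease Evaluation and the TUS. The Month 3 rescue criteria (Section 3.2.3) use the Global Disease Evaluation and the TUS or mRUS. The interim rule (Section 10.5.8) counts successes on the failure definition. None uses weight bearing.

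**7. Size.** The mean bias at a visit would be the share of patients under the order times the mean gap from step 3. The documents give neither, so no estimate is possible.

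**The case against.** The strongest reply is that the options should be read with the instruction above them. Annex 3 describes a performed test, standing or walking or pushing on a table, done as tolerated. Section 3.2.1 says that these categories can be scored in more than one mode and selects the pain-related one. Pain need not be repeated in each cell. This stands for patients who are free to load the limb. It does not help a patient told not to load, who cannot perform the test as tolerated.

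The protocol also concedes that "the current existing scoring method cannot avoid room for subjective patient and physician interpretation". That is a fair disclosure of subjectivity, but a standing order is a fact that can be recorded, not a matter of interpretation.

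Redaction counts for more. Text is blacked out directly after that caveat in Section 3.2.1, within Section 5.4, in the visit lists and in the efficacy sections. A reader might infer that the plan has no rule for scoring restricted patients. The documents do not support that, since such a rule may stand in the redacted text. Nor can it be confirmed that the score is taken at every early visit: the synopsis line is general, and Section 3.2.3 shows that not every measure is available each time.

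A reader might also infer that the wording causes the bias and that new wording would remove it, or that scores 0 to 2 are all restrictions. Step 4 rules out the first. The second overstates the text, because scores 1 and 2 read naturally as ability.

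**Conclusion.** The point holds as a minor one. Both score-0 options are worded as a prohibition and disagree with the mode set in Annex 3 and Sections 2.4.2 and 3.2.1. At any visit where the score is taken under the Section 5.4 order, a 0 can reflect the order, and a later rise can partly mark its lifting.

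This assumes that the score is taken at some visits while the order is in force, and that no redacted passage already handles it. Confidence is medium for that reason. The effect is limited to a non-primary efficacy criterion at visits under restriction, and its size cannot be estimated. Month 6 is probably little affected. A reader might infer that the trial's success rate is at risk; it is not, because the responder definition, rescue criteria and interim rule do not use this score.

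**What to change.** **Main change.** Unless redacted text already does so, add one yes/no item beside the score at each visit: *weight bearing currently restricted by order*. Summarise scores taken under restriction separately from the rest.

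**Supporting change.** In Annex 3 and Section 3.2.1, reword option 0, and for consistency options 1 and 2, as what the patient does when loading as tolerated: 0, holds the limb off the floor or table; 1, touches only, with no body weight; 2, places some body weight. This brings the form into line with its stated mode but does not replace the flag.

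**Cost.** One extra CRF field per visit and the wording of three options in two places. If scoring has begun, two versions of the form will exist among at most 32 treated patients, so the version used must be recorded. Primary endpoint, sample size and interim rule stay as they are.

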## 15.5 ANNEX 4: RADIOLOGICAL EVALUATION: MODIFIED RUS /TUS

The radiological evaluation will be done using conventional X-ray (incl. antero-posterior, latero-lateral) and CT Scan.

The scores used in the imaging interpretation are:

- Score 0 = Callus is Absent and Fracture line is Absent; Fracture is recent (<6 weeks)
- Score 1 = Callus is Absent and Fracture line is Visible
- Score 2 = Callus is Present and Fracture line is Visible
- Score 3 = Callus is Present and Fracture line is Invisible
- Score 4 = Callus is Absent and Fracture line is Absent; Fracture is not recent (>6 weeks)

The minimum mRUS/TUS score is 2 (presence of a fracture line at least on 2 views), maximum is 16 (bone is totally repaired).

**mRUS/TUS SCORE:** Individual cortical score (Lateral, Medial, Anterior and Posterior Cortex)

Modified RUS/TUS					
Lateral Cortex	 0	 1	 2	 3	 4
Medial Cortex	 0	 1	 2	 3	 4
Anterior Cortex	 0	 1	 2	 3	 4
Posterior Cortex	 0	 1	 2	 3	 4

The total mRUS/TUS score (2– 16) is the addition of the individual scores (Lateral, Medial, Anterior and Posterior Cortex)
